After a participant completes the consent process and is deemed eligible for this study, baseline parameters will be obtained. Laboratory tests—including basic metabolic panel (BMP, including serum creatinine), NT-pro-BNP (N-terminal prohormone of brain natriuretic peptide), and troponin—and hemodynamics – heart rate, blood pressure (systolic, diastolic, and mean arterial pressure)—obtained ideally within 24 hours before IP administration will be recorded. If multiple values exist within this time frame, the value closest to time of surgery will be used. Blood for EO concentrations, Proenkephalin A,¹⁸ and TIMP × IGFBP7^{19,20,21} will be drawn prior to investigational drug administration. Patient characteristics including age, sex, comorbidities (hypertension and diabetes) will be noted. Of note, ouabain concentrations take many days to return and will not be known prior to CABG.,

3E. Randomization

After ensuring eligibility, patients will be randomized by the investigational pharmacy. Stratified randomization will be employed using race and sex. Patients will be randomized approximately 24 hours prior to surgery. In the event that surgery is postponed to a later date, patients will be permitted to remain in the study. Digifab will be re-administered according to the usual protocol. If surgery is moved a second time and Digifab had been given, patients will be removed from the study.

3F. Intervention

BTG will provide DigiFab; placebo (saline) will be provided by the pharmacy. In-hospital study patients will be dosed intravenously with 80 mg Digifab or an equivalent volume of fluid the night prior to surgery (approximately 12-15 hours prior to surgery) and again 1 hour preoperatively. The vials will be stored in the hospital investigational pharmacy. Patients being admitted to the hospital on the day of surgery will receive 80 mg Digifab or an equivalent volume of fluid approximately 1 hour prior to surgery.

3G. Post-operative data:

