We will collect blood for endogenous ouabain, Proenkephalin A, and TIMP × IGFBP7 in the immediate post-operative period 0 to 4 hours post-surgery. The ouabain measurement at this time will determine the fraction that is free and that which is bound to DigiFab. This 4 hr post-op sample window provides the only opportunity to obtain critical information concerning the efficacy of the DigiFab immunoneutralization. Total serum ouabain, Proenkephalin A, TIMP × IGFBP7, and creatinine concentrations will also be obtained at 72 +/- 12 hours post-surgery.

Time spent on cardiopulmonary bypass will be noted. Seven days post-operatively, need for any type of renal replacement therapy will be recorded. Lastly, mortality within a seven-day period will be noted.

3H. Data collection

Each variable will be captured and stored in a HIPAA compliant and secure database.

31. Primary endpoint: Changes in GFR will be compared in patients who receive placebo and intervention by ANOVA and, as appropriate, parametric or non-parametric tests. The primary endpoint will compare only patients with the 50% highest baseline (preoperative) concentrations of ouabain.

3J. Secondary endpoints:

- 1. Comparing GFR amongst all patients
- 2. Incidence of AKI comparing the groups (25% decrease from baseline)
- 3. Incidence of renal replacement therapy by 30 days
- 4. Comparing intraoperative and 30 day mortality for placebo vs DigiFab.
- 5. In patients on cardiopulmonary bypass for the longest time (top 50%).
- 6. Comparison of change in Proenkephalin A in patients receiving Digifab and placebo.
- 7. Comparison of change of TIMP × IGFBP7 in patients receiving Digifab and placebo.
- 8. Comparison of GFR in patients receiving one dose and patients receiving two doses of Digifab.

3K. Analysis

Mean comparisons will be made by ANCOVA and, as appropriate, parametric or non-parametric tests. Chi square will be used as indicated. We will control for GFR and sex.

3L. Power

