We postulate that the average patient will have a GFR of 50 which correlates to a creatinine of 129 μ mol/l. Previous studies have shown a post-operative mean increase of 48 μ mol/l with a standard deviation of 76. Therefore, on average, post-operative creatinine should be 177 μ mol/l, which is roughly a GFR of 35. A trial of 62 patients per group (top half of elevated ouabain concentrations) should have a power of >70% to detect a 36 μ mol/l difference in plasma creatinine, i.e., a creatinine of 141 μ mol/l (177-36). A creatinine of 141 μ mol/l correlates to a GFR of 45—a ~25% increase in GFR.

4. Risks

The primary risk associated with this study includes all of the potential adverse effects of DigiFab including: anaphylactic and anaphylactoid reactions, delayed allergic reactions, and a febrile response to immune complexes formed. However, since the Fab fragment of the antibody lacks the antigenic determinants of the Fc region, this should pose a reduced immunogenic threat. Of note, no patients during the clinical trials experienced an anaphylactic event. Patients with allergies to sheep protein would be at particular risk. In a registry of 717 adult patients receiving DigiFab, 6 had a probable or possible adverse reaction to the medication. All were symptomatically treated successfully²². Study participants will be monitored closely for potential adverse effects in the perioperative, operative, and post-operative setting. If an anaphylactic

reaction occurs, epinephrine, steroids, an H2 blocker, and diphenhydramine will be given as appropriate. Each blood draw carries the risk of pain associated with the venous puncture. As this is the first use of DigiFab in this patient population, unknown side effects are possible.

Data Safety and Monitoring Board

There will be an independent Data Safety and Monitoring Board (DSMB) which will assess the safety of the trial after 62 patients (first 25% of patients are enrolled). An unblinded coordinator will provide the board with all adverse events and deaths to investigate. The DSM board will evaluate the cause of deaths and allergic reactions. The panel will consist of [name], [name], [name], and a statistician.

5. Benefits

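### Sections 3I and 3K name different models for the primary comparison, and neither includes race, which is a randomization stratifier (minor)

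*Combined protocol and SAP*

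**What the plan says.** - **3I, Primary endpoint:** "Changes in GFR will be compared in patients who receive placebo and intervention by ANOVA and, as appropriate, parametric or non-parametric tests". No covariates are named. The analysis set is restricted: "The primary endpoint will compare only patients with the 50% highest baseline (preoperative) concentrations of ouabain".
- **3K, Analysis:** "Mean comparisons will be made by ANCOVA and, as appropriate, parametric or non-parametric tests", and then "We will control for GFR and sex". It does not say that the GFR meant is the baseline value, although that is the likely meaning.
- **3E, Randomization:** "Stratified randomization will be employed using race and sex".
- **3D, Enrollment and Baseline:** "ouabain concentrations take many days to return and will not be known prior to CABG". Ouabain therefore cannot be a stratifier.
- **3G, Post-operative data:** "creatinine concentrations will also be obtained at 72 +/- 12 hours post-surgery". The Timeline (section 11) also records creatinine at 0-4 hours.
- **3L, Power:** 62 patients per group "should have a power of >70% to detect a 36" μmol/l creatinine difference, with an SD of 76.

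No section says whether 3I or 3K governs the primary test. Race is in no analysis statement. Alpha and sidedness are not given.

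**The concern.** The primary endpoint is a comparison of means, so 3I and 3K both apply to it, and they name different models. Both also allow other parametric or non-parametric tests where appropriate, with no rule for choosing. As written, the primary p-value could come from an unadjusted ANOVA, an adjusted ANCOVA or a rank test.

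Separately, the trial balances its arms on race and sex, but 3K adjusts for sex alone and 3I for neither. The usual advice is to analyse by the factors used in randomization. Otherwise, variation that the design or model could remove stays in the error term. Planned power is only about 74%, so any cheap gain is worth having.

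**Working it through.** **1. The plan's own power figure.** The inputs from 3L are 62 per group, a difference of 36 and an SD of 76. Alpha is not stated; I assume 5%.

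- d = 36/76 = 0.474
- Noncentrality = 36 / (76 × √(2/62)) = 2.637
- Noncentral t, 122 df: 74.4% two-sided, 83.6% one-sided

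Both results satisfy the stated >70%, so the figure reproduces. It corresponds to an unadjusted two-group comparison of creatinine. It therefore settles neither the choice between ANOVA and ANCOVA nor the sidedness.

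**2. Power lost by omitting race.** Let p be the share of patients in one race category and b the race effect in residual SDs. Neither is in the documents; I take p = 20-40% and b = 0 to 1.0. Leaving race out multiplies the residual SD by √(1 + p(1−p)b²) and divides the noncentrality by the same factor. Example with p = 0.4 and b = 1: √1.24 = 1.114, 2.637/1.114 = 2.368, power 65.2%.

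The simulation used 250 patients, permuted blocks of 4 within race × sex strata, and the top 125 by ouabain analysed. It had 20,000 trials per setting and compared the 3K model with and without race. Ouabain was taken as unrelated to outcome and d = 36/76 as the effect in residual SDs.

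| Race effect (SD) | On the 76 μmol/l scale | Share of residual variance | Power without race, formula | Power without race, simulated | Power with race, simulated | Gain from adding race |
|---|---|---|---|---|---|---|
| 0 | 0 | 0 | 74.4% | 74.0-74.4% | 73.8-74.1% | about -0.2 points |
| 0.3 | about 23 | 1.4-2.1% | 73.5-73.8% | – | – | under 1 point |
| 0.5 | 38 | 3.8-5.7% | 72.0-72.8% | 71.4-72.9% | 73.4-73.9% | 1-3 points |
| 1.0 | 76 | 13.8-19.4% | 65.2-68.1% | 65.0-68.0% | 73.7-73.8% | 5-9 points |

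The last column spans repeated simulation runs, including separate runs at 0.3 SD. Variance share is p(1−p)b² / (1 + p(1−p)b²). A simulation on the GFR scale gave similar or smaller changes: -0.4 to 0, +0.7 to +1.8 and +4.1 to +5.7 points at 0, 0.5 and 1.0 SD of the creatinine rise.

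**3. Type I error without race.** It was 4.8-5.0% at zero race effect, 4.5-4.9% at 0.5 SD and 3.9-4.4% at 1.0 SD. With race in the model it was 4.8-5.2%. Omission is mildly conservative, not anti-conservative.

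**4. Race balance in the primary subset.** With near-perfect balance in all 250, a random half of 125 has a between-arm difference in race share with variance of about 2p(1−p)/125. The 95% limit is 1.96 × √(2 × 0.16/125) = 9.9 points at p = 20% and 1.96 × √(2 × 0.24/125) = 12.1 points at p = 40%. Simulation gave 10-12 points in the subset and 1.6 points in all 250.

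**5. ANOVA on change against ANCOVA (GFR, sex).** On simulated GFR the two differ by at most 0.7 points of power if sex has no effect. ANCOVA gains 0.7-2.1 points if sex has an effect of 0.5 SD. They disagree on p<0.05 in 1.8-5.4% of trials, and in up to 6.8% if sex is prognostic. Each alone has type I error of 4.2-5.2%. Taking the better of the two after seeing results gives 4.8-6.3%.

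**The case against.** The strongest reply is that nothing here threatens validity, and that 3K is the natural governing section. It is headed Analysis, follows the endpoint lists and covers mean comparisons without exception. 3I is silent on covariates and does not rule them out. A reader might infer that the primary analysis is definitely unadjusted; the text does not support that. What stands is that no sentence links the two sections.

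A reader might also infer that weaker race balance in the ouabain subset makes the test unreliable. It does not. That imbalance is chance imbalance, and the standard error already allows for it. Omitting race is in fact less conservative in the subset (4.5-4.9% and 3.9-4.4% at 0.5 and 1.0 SD) than it would be if stratification held exactly within the analysed patients (4.3-4.7% and 3.2-3.6%).

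Finally, the larger power losses need very large race effects. If 76 is taken as the residual SD, 0.5 SD is 38 μmol/l, already above the 36 μmol/l target effect. 1.0 SD is 76 μmol/l, above the whole expected surgical rise of 48. Nothing in the documents suggests effects of that size. This objection stands, and it is why the point is minor.

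**Conclusion.** The point holds as a minor matter of pre-specification and efficiency. The primary comparison has two stated models with no sentence saying which applies, and a randomization stratifier is missing from both. The likely power gain from adding race runs from slightly negative to about 3 points. The 5-9 point gain belongs to an extreme case. It would be wrong to conclude from the 65-68% figures that the trial falls short of its stated >70% power: they depend on an assumed race effect of 1.0 SD.

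The split between ANOVA and ANCOVA matters little unless the model is chosen after results are seen. The commitment in section 8 to keep investigators blinded until data are final limits that risk but does not remove it.

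These sizes rest on assumed race shares, race effects and block size, on ouabain being unrelated to outcome, and on a two-sided 5% level.

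**What to change.** - **3I:** state that the primary comparison is the ANCOVA of 3K: post-operative GFR on treatment, adjusted for baseline GFR, sex and race, in patients in the top half of baseline ouabain. With baseline GFR as a covariate, modelling the change or the post-operative value gives the same treatment estimate, so the endpoint is not altered.
- **3K:** replace the covariate list with baseline GFR, sex and race. Use the race categories of the randomization, and pool sparse categories before unblinding.
- **Both sections:** keep any rank-based test as a sensitivity analysis, so that the primary test is not chosen after seeing results.
- **Sponsor to confirm:** the time point (72 ± 12 hours is the later creatinine in 3G, but 3I names none), and alpha and sidedness, which are not stated for the primary test.

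The cost is wording. Race is already needed for the randomization, so no new data or patients are required. The model uses 1-3 more degrees of freedom. If race is not prognostic, that costs 0.2-0.3 points of power with one race term and 0.8 points with three.

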We plan to conduct a randomized double-blinded study investigating the role of DigiFab in patients with elevated risk of acute kidney injury undergoing CABG surgery. Patients who are undergoing CABG, meet the inclusion criteria, and provide consent will be enrolled in this study and randomized to either DigiFab arm or the placebo (vehicle) arm. The number of patients to be consented will be enough to achieve two hundred and fifty evaluable participants. The number consented will not be more than 350 patients. The study involves a follow up period of 72 hours post CABG surgery.

3A- Recruitment

All patients awaiting non-emergency CABG surgery will be considered for this study. Patients with high risk of developing AKI post CABG will be included in this study. High risk of AKI will be defined as one of the following: GFR >15 but below 60 (must be >36 hours after receiving any contrast, but within two weeks of signing consent) or a history of diabetes mellitus. Diabetes will be defined as a past diagnosis or a current hemoglobin a1c of \geq 6.5%.

3B. Inclusion Criteria

Each patient must meet all the following criteria to be enrolled in this study:

- Patient provided informed consent
- Male or female > 18 years of age
- Undergoing CABG and one of the following:
 - GFR (Cockcroft-Gault) less than 60 (should be > 36 hours after receiving any contrast, but within two weeks of signing consent)
 - o Past diagnosis of Diabetes or current Hemoglobin A1c of \geq 6.5%

3C . Exclusion criteria

A patient who meets any of the following criteria will be excluded from this study:

- AKI defined as:
 - o Decrease in GFR > 25% of baseline based on RIFLE criteria¹⁷
- Received contrast within the past 36 hours of IP administration
- Prior kidney transplantation
- Prior adverse reaction to DigiFab
- Received Digoxin within the past 30 days

- Has allergy to papaya, papain, or sheep proteins
- GFR < 15 (within two weeks of signing consent and > 36 hours after receiving contrast)

Calculation of Creatinine Clearance (Ccr; Cockcroft-Gault Formula)

 $C_{Cr} = \{((140 - age) \times weight)/(72xS_{Cr})\} \times 0.85 \text{ (if female)}\}$

 C_{Cr} (creatinine clearance) = mL/minute

Age = years; Weight = kg

SCr (serum creatinine) = mg/dL

3D. Enrollment and Baseline

Patients awaiting surgery in the hospital or having elective surgery and initially seen as outpatients will be eligible for this study.

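### Secondary endpoints 6 and 7: the named covariates leave out each marker's own pre-dose value, so a literal analysis gives up precision and carries chance baseline imbalance into the estimate

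*Combined protocol and SAP*

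**What the plan says.** Section 3J defines item 6 as "Comparison of change in Proenkephalin A in patients receiving Digifab and placebo" and item 7 as "Comparison of change of TIMP × IGFBP7 in patients receiving Digifab and placebo".

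Section 3K gives one method statement for every comparison of means: "Mean comparisons will be made by ANCOVA and, as appropriate, parametric or non-parametric tests". The covariates follow in one sentence: "We will control for GFR and sex". Nothing else in the document adds a marker's own baseline to the model for items 6 and 7.

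The baseline exists. Section 3D says that blood for both markers "will be drawn prior to investigational drug administration", and item 2 of the section 11 timeline repeats this. Both markers are measured again at 0–4 hours and at 72 ± 12 hours after surgery (section 3G; timeline items 6 and 7). Items 6 and 7 do not say which of these samples defines the change.

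On balance between arms, section 3E says: "Stratified randomization will be employed using race and sex". Neither marker is a stratification factor.

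**The concern.** A change score subtracts the whole baseline value, which amounts to fixing the slope of follow-up on baseline at 1. If the true slope differs from 1, the subtraction leaves noise that regression on the baseline would remove. A chance difference between arms at baseline then also moves the estimated treatment effect.

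For the GFR endpoints, adjusting for GFR would cover the outcome's own baseline, if baseline GFR is what is meant. Endpoints 6 and 7 have no such covariate in the list. At stake is the precision of the plan's two kidney-biomarker comparisons, for which no power is stated, using samples that will be drawn anyway.

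**Working it through.** **The plan's own figure.** Section 3L gives power above 70% for 62 per group, a creatinine difference of 36 µmol/l and an SD of 76. Assuming two-sided 0.05, which the plan does not state, the standard error is 76 × √(2/62) = 13.65. Then 36/13.65 = 2.64, and power is Φ(2.64 − 1.96) = 75% (74% by noncentral t). The figure reproduces. It belongs to the primary comparison; endpoints 6 and 7 have none.

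**Inputs for endpoints 6 and 7.** Section 3 plans for "two hundred and fifty evaluable participants", so 125 per arm if allocation is 1:1 (assumed; the ratio is not stated). The marker SDs s0 and s1 and the correlation r are not in the documents and are varied below. GFR and sex are left out at first.

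**Formulas.**
- Var(change) = s0² + s1² − 2·r·s0·s1
- Var(ANCOVA on own baseline) = s1²·(1 − r²)
- Difference = (s0 − r·s1)², never negative, and zero only when the slope r·s1/s0 equals 1

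Example with s0 = s1 = 1 and r = 0.5: Var(change) = 2 − 1 = 1.00, Var(ANCOVA) = 1 − 0.25 = 0.75, ratio 1.33.

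**Excess variance of the change analysis over own-baseline ANCOVA**

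| s1/s0 | r = 0.3 | r = 0.5 | r = 0.7 |
|---|---|---|---|
| 1 | 54% | 33% | 18% |
| 1.25 | 28% | 12% | 2% |
| 1.5 | 15% | 4% | 0.2% |
| 2 | 4% | 0% | 8% |

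With equal SDs, 125 per arm then does the work of 125/1.538 = 81, 125/1.333 = 94 and 125/1.176 = 106 per arm. Outside this range, r = 0.9 gives 5% with equal SDs, but 84% when s1/s0 = 2, because the slope is then 1.8.

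**Power**, for an assumed effect of 0.3 post-operative SD, 125 per arm, two-sided 0.05:

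| s1/s0 | r | Change | Own-baseline ANCOVA |
|---|---|---|---|
| 1 | 0.3 | 51.5% | 69.7% |
| 1 | 0.5 | 65.6% | 77.9% |
| 1 | 0.7 | 86.2% | 91.1% |
| 1.5 | 0.3 | 64% | 70% |
| 1.5 | 0.5 | 76% | 78% |

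**Chance imbalance.** One standard error of the baseline difference is √(2/125) = 0.126 baseline SD. The change estimate moves by (1 − slope) times the imbalance. With equal SDs:
- r = 0.5: 0.5 × 0.126 = 0.063 SD. The ANCOVA standard error is √(0.75 × 2/125) = 0.110, so the shift is 0.58 of it.
- r = 0.8: 0.2 × 0.126 = 0.025 SD, or 0.33 of the ANCOVA standard error.

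**Does GFR adjustment do the job?** GFR was put into both models with equal SDs, assumed marker–GFR correlations of 0 or −0.5 to −0.7, and r of 0.5 to 0.8. The variance ratio was 1.02 to 2.00. GFR does not stand in for the marker's own baseline.

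**The case against.** The strongest objection is that 3K is silent on the marker baseline rather than opposed to it. ANCOVA on a change outcome often includes the baseline, and the authors may intend that. This stands in part. A reader might infer that the plan has chosen a plain change-score analysis; the wording does not support that. But 3K does name its covariates, the marker baseline is not among them, and alternative tests are allowed as appropriate. An analyst working from the text could fit arm, GFR and sex, or no covariates at all.

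The contrast with the GFR endpoints is also not firm. Section 3K does not say that its GFR covariate is the baseline value, and section 3I assigns the primary comparison to ANOVA. The point does not depend on that contrast.

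A reader might further infer that the change score loses precision whenever r is below 1. That is true with equal SDs but not in general: with s1/s0 = 2 and r = 0.5 the loss is nil. Surgery could plausibly widen the post-operative spread, and the documents do not settle it.

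A reader might also infer bias or an inflated false-positive rate. Neither follows. Under randomisation the expected baseline difference is zero, so the estimate is unbiased on average and type I error is controlled. The imbalance error is conditional on the draw that occurs.

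Finally, these are two of eight secondary endpoints. The primary analysis and the sample size are untouched.

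**Conclusion.** The point holds as a question of precision and of conditional error from chance imbalance. Read literally, 3K omits a covariate that the trial will already have and that the randomisation does not balance. Own-baseline ANCOVA has variance no larger than the change analysis, apart from the negligible cost of estimating one more coefficient, and smaller variance unless the slope is 1.

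The size cannot be fixed from the documents. The 54% figure is the upper end of the assumed range of r from 0.3 to 0.7, not an expected loss, and over part of that range the loss is close to zero. The power figures also assume a 0.3 SD effect, 1:1 allocation and two-sided 0.05. The improvement is worth making because it is free, but it is not critical to the trial's main conclusion.

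**What to change.** In 3K, state that endpoints 6 and 7 are analysed by ANCOVA with arm, the same marker's pre-dose value, baseline GFR and sex. Name the post-operative sample (0–4 h or 72 h) used for each comparison.

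The endpoint can still be reported as change. Once the pre-dose value is in the model, the arm coefficient is the same whether the outcome is the change or the post-operative value on the same scale.

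A log scale is optional. The documents give no distributional information that requires it; if it is wanted, it should be chosen before unblinding.

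The cost is a sentence or two of analysis text and one residual degree of freedom per model. No extra samples, visits or patients are needed. Making the change before unblinding also removes a later choice between models.

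### Secondary endpoint 8 compares one-dose with two-dose DigiFab patients, but dose number is not randomised and control for GFR and sex alone may leave differences in patient mix

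*Combined protocol and SAP*

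**What the plan says.** Section 3 states that patients are "randomized to either DigiFab arm or the placebo (vehicle) arm", and section 3E stratifies that randomisation by race and sex. No section randomises or stratifies by number of doses.

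Section 3F sets the number of infusions by admission route, in both arms. Patients already in hospital are dosed the evening before surgery (about 12-15 hours ahead) and again 1 hour before it. Patients admitted on the day of surgery are dosed once, about 1 hour before. Section 11, item 3, makes the evening dose conditional on being more than 36 hours past contrast, and lets some inpatients have only the immediate pre-operative dose so that they meet entry requirements. This ties in with the exclusion in section 3C: "Received contrast within the past 36 hours of IP administration".

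Item 8 of section 3J is then a "Comparison of GFR in patients receiving one dose and patients receiving two doses of Digifab". On adjustment, section 3K says only: "We will control for GFR and sex". Section 3D collects more than this: "Patient characteristics including age, sex, comorbidities (hypertension and diabetes) will be noted", and NT-pro-BNP and troponin are measured at baseline as well. Item 8 is listed with the randomised secondary comparisons and is not marked as non-randomised or exploratory.

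**The concern.** Item 8 compares two groups formed by how and when patients came to hospital. Inpatients awaiting CABG and patients coming in on the day may differ in acuity, cardiac markers or comorbidity, and any of these could affect post-operative GFR. Whatever GFR and sex do not capture would appear as an effect of dose number, or would hide a real one. A reader who sees item 8 among the randomised comparisons could take it as evidence on one dose versus two, which it cannot supply alone.

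There is also a gap in definition. After a first postponement of surgery, "Digifab will be re-administered according to the usual protocol" (section 3E). A same-day patient who is dosed, postponed and re-dosed has then had two doses, and an inpatient can reach three or four. Item 8 does not say how such patients are classed.

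**Working it through.** **How dose number is assigned.** The main route is admission status (section 3F). The contrast route is narrow. Taking the 36-hour rule with the dose times in sections 3F and 11:

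- The pre-operative dose 1 hour before surgery is allowed if contrast was more than 36 + 1 = 37 hours before surgery.
- The evening dose is allowed only if contrast was more than 36 + 12 = 48 to 36 + 15 = 51 hours before surgery.
- So only inpatients with contrast between about 37 and 48-51 hours before surgery can lose the evening dose, a window of 11 to 14 hours.

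**What each comparison estimates.**

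- Direct (item 8): DigiFab two-dose minus DigiFab one-dose = dose effect + residual difference in patient mix.
- Interaction: (DigiFab minus placebo, two infusions) minus (DigiFab minus placebo, one infusion). Mix differences common to both arms cancel. What remains is the dose effect plus any difference in DigiFab's effect between the two kinds of patient.

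**The plan's own figure.** Section 3L gives 62 per group, a difference of 36 µmol/l, SD 76 and power above 70%. SE = 76 × √(2/62) = 13.65; 36/13.65 = 2.637; power = Φ(2.637 − 1.96) = 75.1%, at an assumed two-sided 5%. The figure is reproduced. The plan states no figure for item 8.

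**Illustration for item 8.** From the documents: SD 76 µmol/l (section 3L) and "two hundred and fifty evaluable participants" (section 3). Assumed: 125 DigiFab patients (250/2; the allocation ratio is not stated), two-sided 5%, one-dose shares of 50%, 25% and 10%, and residual gaps of 10 and 20 µmol/l. The 36 µmol/l is borrowed from section 3L as a yardstick.

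With n₁ and n₂ the one- and two-dose numbers, n₁ + n₂ = 125:

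- Direct SE = 76 × √(1/n₁ + 1/n₂)
- Interaction SE = 76 × √(2/n₁ + 2/n₂), that is, √2 = 1.414 times as large
- Rejection rate for a shift b = Φ(b/SE − 1.96) + Φ(−b/SE − 1.96)

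| | 50% | 25% | 10% |
|---|---|---|---|
| n₁ | 62.5 | 31.25 | 12.5 |
| Direct SE (µmol/l) | 13.6 | 15.7 | 22.7 |
| Direct: significant with no dose effect, gap 10 | 11.4% | 9.8% | 7.3% |
| Direct: significant with no dose effect, gap 20 | 31.3% | 24.7% | 14.3% |
| Direct: power for 36, no gap | 75.4% | 63.1% | 35.5% |
| Direct: power for 36, opposing gap 10 (net 26) | 48.1% | 38.1% | 20.9% |
| Interaction SE (µmol/l) | 19.2 | 22.2 | 32.0 |
| Interaction: power for 36 | 46.5% | 36.8% | 20.2% |
| Interaction: significant if DigiFab's effect differs by 20 between routes for reasons other than dose | 18.0% | 14.7% | 9.6% |

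**Why not on the GFR scale.** Item 8 is a GFR endpoint, but section 3L gives no GFR SD. Its three creatinine-GFR points (129 and 50; 141 and 45; 177 and 35) imply different ones: 76 × 10/36 = 21.1, 76 × 15/48 = 23.75 and 76 × 5/12 = 31.7 mL/min. A GFR-scale rate would depend on which pair was used.

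**The case against.** The case against has several sound parts. Only non-emergency CABG is eligible, and pre-operative AKI and GFR below 15 are excluded (sections 3A and 3C), which narrows the differences between inpatients and same-day admissions. The GFR used for eligibility is Cockcroft-Gault, which contains age, weight and sex; if section 3K means the same measure, age is partly covered. The plan says only that a comparison will be made and claims no causal dose effect. Item 8 is the last of eight secondary endpoints, with no alpha, decision rule or sample size. The suggested interaction is less precise and asks a somewhat different question from the one in item 8. All of this stands and keeps the point at low severity. It does not make the groups comparable: admission route, contrast timing and the cardiac markers remain outside the stated adjustment.

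A reader might go further in three ways that the documents do not support:

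- *That item 8 is biased by a known amount or in a known direction*, for example that two doses will look worse because inpatients are sicker. The documents give no outcomes, risk profile or patient numbers by route. The rates above follow from assumed gaps and shares, use the SD of a post-operative creatinine increase from previous studies, and do not show that a gap exists.
- *That recent contrast is a main driver of dose number.* It can act only within the 11- to 14-hour window, and under section 3C nobody should be dosed within 36 hours of contrast.
- *That the trial's main result is compromised.* Both randomised arms follow the same infusion schedules, so DigiFab versus placebo is not confounded by route.

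**Conclusion.** The point holds as a low-severity improvement. As written, item 8 compares non-randomised groups with adjustment for GFR and sex only, and neither a difference nor its absence can be attributed to number of doses. This conclusion rests on the allocation rules in sections 3, 3E, 3F and 11 and on section 3K, not on any calculation. The calculation adds only that moderate residual gaps, if present, could matter in either direction: false significance in about 7% to 31% of trials over the assumed range, and power for a real 36 µmol/l difference reduced from about 36-75% to 21-48% by an opposing gap of 10 µmol/l. The effect is confined to one secondary endpoint.

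**What to change.** 1. Label item 8 exploratory and non-randomised.
2. Record each patient's planned one- or two-infusion schedule in both arms at randomisation. Section 3E gives the time point: "Patients will be randomized approximately 24 hours prior to surgery". Grouping by planned schedule also settles how patients re-dosed after a postponement are classed.
3. Report the DigiFab-minus-placebo difference in GFR within each planned schedule, and the treatment-by-schedule interaction with its 95% CI. State that this shows whether the effect differs by schedule and is not a pure dose effect.
4. If the direct one-dose versus two-dose comparison is kept, report it with a 95% CI as non-randomised. Adjust it also for age, diabetes, hypertension, NT-pro-BNP and troponin, as far as group size allows; at a 10% share there would be only about 12 one-dose patients.
5. Separately, section 3F states two doses for in-hospital patients with no exception, while section 11, item 3, gives some inpatients only the pre-operative dose. The two passages must be reconciled.

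**Cost.** One recorded field and a reworded endpoint, with no extra patients or procedures. The loss is precision: under the assumptions above, 80% power for the interaction would need a difference of (1.96 + 0.84) × SE, about 54, 62 and 90 µmol/l at one-dose shares of 50%, 25% and 10%. It can therefore only be exploratory.
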